³ Need for mechanical ventilation/ECMO, including ventilator settings, or supplemental oxygen, including mode of oxygen delivery. ⁴ Collected until Day 28 or hospital discharge, whichever occurs earlier 5 ABGs are collected daily while in ICU/CCU, and recorded if performed as part of routine care outside of ICU/CCU, until Day 28 or hospital discharge, whichever occurs earlier ⁶ if subject is discharged, these visit do not apply; subject should return for infusion visits only. ⁷ If a subject is discharged from hospital before Day 28, and unwilling to return for visits and infusions in an outpatient setting, visits may be conducted remotely for assessment of vital status and safety. If a subject is lost to follow-up after hospital discharge, vital status may also be obtained from public records. 8 Visit windows, for outpatient dosing visits ONLY: visit window for Day 14: +/- 2 days. Visit window for Day 28: +/- 3 days.

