5.1 Statistical Methodology

There will be no treatment comparison analysis performed for this early terminated study.

Baseline is defined as the last value on or before the first infusion.

Continuous variables will be summarized using descriptive statistics: n, mean, standard deviation (SD), standard error (SE), median, 25th and 75th percentile, minimum, and maximum. The 2-sided 95% confidence interval for the treatment group mean will be presented as appropriate. Categorical variables will be tabulated by frequency count and percentage. The confidence interval for the proportions for each treatment group will be calculated using the Clopper-Pearson method as appropriate.

The Clopper-Pearson exact 95% CIs for the dichotomous parameters will be from SAS FREQ procedures with option BINOMIAL (EXACT). The 95% CIs for means of normally distributed parameters will be from appropriate SAS procedures such as PROC MEANS.

Analyses will be performed using SAS® Version 9.3 or higher.

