5.2.1 Intent-to-Treat (ITT) Population

The ITT population is defined as all randomized subjects. Subjects will be analyzed according to the treatment as randomized.

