9 EFFICACY ANALYSES

Efficacy data will be summarized descriptively based on observed data for the ITT population. There will be no imputation performed for the missing endpoint value.

9.1 Primary Efficacy Endpoint - Proportion of Subjects who Never Received Mechanical Ventilation and/or ECMO and Alive at Day 28

Proportion of subjects never received mechanical ventilation and/or ECMO and alive at Day 28 will be summarized based on observed data.

9.2 Proportion of Subjects Alive, Discharged, and not on Supplemental Oxygen, Proportion of Subjects who Never Received Mechanical Ventilation and/ or ECMO and Alive, and Proportion of Subjects Deceased

Proportion of subjects alive, discharged home, and not on supplemental oxygen at Day 28, proportion of subjects never received mechanical ventilation and/ or ECMO and alive at Day 14, and proportion of all-cause deaths at Day 28 will be summarized descriptively based on observed data.

9.3 Time to Recovery, Time to Mechanical Ventilation/ECMO or All-cause Mortality, and Time to death

- Time (number of days) from randomization to recovery by Day 28 based on NIAID 8-point ordinal scale where recovery is defined as the first day on which the patient satisfies one of the following three categories from the ordinal scale: (1) Not hospitalized, no limitations on activities; (2) Not hospitalized, limitations on activities and/or requiring home oxygen; (3) Hospitalized, not requiring supplemental oxygen, no longer requiring medical care (used if hospitalization was extended for infection-control reasons)

Subjects without the event will be censored at the date of last NIAID 8-point ordinal scale assessment.

- Time (number of days) from randomization to mechanical ventilation/ECMO or all-cause mortality by Day 28

For subjects who did not have the event, the last known assessment date of mechanical ventilation/ECMO use or survival status, whichever later will be defined as the censoring date.

- Time (number of days) from randomization to death from any cause by Day 28

For subjects who are alive, the recorded date of last known alive, last contact date, or the date of the last clinic visit, whichever latest will be defined as the censoring date.

The number of days of the above endpoints will be summarized descriptively as appropriate.

9.4 Clinical Status Based on the NIAID 8-point Ordinal Scale at Day 28

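### Does SAP 9.1 need a rule for subjects whose Day-28 primary outcome is unknown?

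*SAP*

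**What the plan says.** The SAP was approved after the sponsor stopped the trial with 22 subjects randomised (SAP 1). Its efficacy section opens with two general rules: "Efficacy data will be summarized descriptively based on observed data for the ITT population", and "There will be no imputation performed for the missing endpoint value". SAP 9.1 then gives the primary endpoint one sentence: "Proportion of subjects never received mechanical ventilation and/or ECMO and alive at Day 28 will be summarized based on observed data". SAP 5.2.1 fixes the population: "The ITT population is defined as all randomized subjects".

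SAP 5.1 reports categorical variables as counts with percentages, takes exact Clopper-Pearson intervals for each arm from the SAS FREQ procedure, and rules out any treatment comparison.

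Two neighbouring sections are more explicit than 9.1. The ordinal-scale table in SAP 9.4 has a row for missing values. SAP 9.3 gives a censoring date for the time-to-event form of the same composite: "For subjects who did not have the event, the last known assessment date of mechanical ventilation/ECMO use or survival status, whichever later".

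The protocol's Appendix 1 limits what is known after discharge. Footnote 4, on SpO2 and on oxygen and ventilation needs, reads: "Collected until Day 28 or hospital discharge, whichever occurs earlier". Footnote 7 allows remote visits for vital status and safety, and adds: "If a subject is lost to follow-up after hospital discharge, vital status may also be obtained from public records".

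**The concern.** The two sides of this composite are settled at different times. A failure (ventilation, ECMO or death) is known on the day it happens. A success is known only at Day 28. If observed data means subjects with a determined outcome, a subject lost event-free leaves both numerator and denominator, while a subject who failed before being lost remains. The proportion then falls although no failure has been added, and its base is no longer all randomised subjects. Two arms with the same number of failures could show different figures only because one lost more subjects.

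One class has no evident place in 9.1: a subject lost after discharge whose survival is known only from public records. Being alive at Day 28 is established; later ventilation is not. Under SAP 9.3 the later of the two dates applies, so survival alone carries this subject event-free to Day 28, whereas 9.1 is silent. At stake is whether two programmers following the same SAP would print the same primary proportion.

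**Working it through.** **Inputs.** 22 randomised (SAP 1) at 1:1 (SAP 3). I assume 11 per arm, because the split is not given. The documents give neither the number of failures nor the number unresolved, so 2 or 4 failures (f) and 0 to 3 unresolved (u) are illustrations. The plan states no loss figure to reproduce. Its design figure, about 80% power with 65 per arm (Protocol 9.1), comes back as 80.1% with Fisher's exact test and is not in dispute.

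**Step 1: size per arm.** Complete-case = (11 − f − u)/(11 − u). Keeping all 11, with the unresolved counted first as failures and then as successes, gives (11 − f − u)/11 to (11 − f)/11, a width of u/11, or 9.1 points per unresolved subject.

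| f | u | Complete-case | Exact 95% CI | All-11 range |
|---|---|---|---|---|
| 2 | 0 | 9/11 = 81.8% | 48.2–97.7 | 81.8 |
| 2 | 1 | 8/10 = 80.0% | 44.4–97.5 | 72.7–81.8 |
| 2 | 2 | 7/9 = 77.8% | 40.0–97.2 | 63.6–81.8 |
| 2 | 3 | 6/8 = 75.0% | 34.9–96.8 | 54.5–81.8 |
| 4 | 0 | 7/11 = 63.6% | 30.8–89.1 | 63.6 |
| 4 | 1 | 6/10 = 60.0% | 26.2–87.8 | 54.5–63.6 |
| 4 | 2 | 5/9 = 55.6% | 21.2–86.3 | 45.5–63.6 |
| 4 | 3 | 4/8 = 50.0% | 15.7–84.3 | 36.4–63.6 |

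Arms with equal failures and 0 versus 2 unresolved differ by 4.0 points (f = 2) or 8.1 points (f = 4, unrounded). The interval for 9/11 alone spans 97.7 − 48.2 = 49.5 points.

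**Step 2: expected drift if loss is unrelated to outcome.** Take constant hazards over 28 days, true success p, and 28-day loss probability L (assumed). Let a = −ln p and b = −ln(1 − L). Then determined successes = p(1 − L), determined failures = [a/(a + b)] × [1 − p(1 − L)], and complete-case = successes/(successes + failures). For p = 65% and L = 10%: successes 0.585; failures 0.4308/0.5361 × 0.415 = 0.333; complete-case 0.585/0.918 = 63.7%. Over L = 5%, 10% and 20% the results are 64.4%, 63.7% and 62.2% for a true 65%, and 84.7%, 84.3% and 83.5% for a true 85% (the two rates in Protocol 9.1). At 10% loss the drift is 1.3 and 0.7 points. If loss is related to outcome, the direction is not known.

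**Step 3: can a reader see it?** The table will carry a count and a percentage to one decimal (SAP 5.1, 5.3), and SAP 6 gives the number randomised by arm. A printed 7 (77.8%) means 7/0.778 = 9 subjects in the base; with 11 randomised, 11 − 9 = 2 are unresolved, and the range 7/11 to 9/11 follows. This fails only for a zero count, where SAP 5.3 suppresses the percentage.

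**Step 4: who could be unresolved?** Subjects in hospital at Day 28, or reached in person or by phone, are not. Appendix 1 schedules survival, ICU and discharge status and adverse events through four weeks after the last dose, and inpatient hospitalisation makes an event serious (Protocol 8.2.2), so readmission is capturable for anyone contacted. Termination need not have cut follow-up: a subject randomised on 19 February 2021 would reach Day 28 on 18 March, 46 days before SAP approval on 3 May, and no text says follow-up stopped.

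**The case for a change.** The best case for a change is that the words bar filling in a value but do not define when a two-part outcome counts as observed. Naming ITT alongside observed data lets a programmer defend either denominator, and Step 3 works only on the complete-case one: a printed 7 (63.6%) on a base of 11 would mix failures with unresolved subjects. SAP 9.4 and 9.3 show that the authors could be explicit, and a sentence costs almost nothing. In SAP 9.3, carrying a subject event-free on survival alone is hard to defend.

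The missing definition stands, and so does the asymmetry. But counting unresolved subjects as non-successes is itself an imputation, which the lead-in excludes, so complete-case is what an analyst would sensibly run. If the other base were used, the listings of all collected data (SAP 5) would still allow a recount. Reporting both extremes as a required output would bring back the kind of imputation that the SAP chose not to do. The 9.3 date feeds only a descriptive summary of days, and nothing shows that any of the 22 subjects depends on it.

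**Conclusion.** This is missing detail that analysts can fill sensibly, not a flaw that needs an amendment. SAP 9.1 does not define an observed composite or state its base, and on the natural reading event-free losses drop out while earlier failures stay. With 11 per arm assumed, one to three unresolved subjects lower the printed proportion by 1.8 to 6.8 points with 2 failures (81.8% to 80.0–75.0%) and by 3.6 to 13.6 points with 4 failures (63.6% to 60.0–50.0%), inside exact intervals roughly 50 points wide or more. Under unrelated loss at an assumed 10%, the expected drift is about one point. The number unresolved is not documented and may be zero, in which case nothing moves.

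No conclusion rests on the figure: it is a per-arm description in a terminated study with no treatment comparison, and the planned outputs let a reader work back to the unresolved number in the usual case. The later-date rule in SAP 9.3 is questionable but is not shown to alter any result.

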9.4. Statistical Methods

The analysis of the proportion of subjects who never received mechanical ventilation and/or ECMO and are alive at Days 14 and 28, the proportion of subjects alive, discharged home, and not on supplemental oxygen at Day 28, proportion of subjects' clinical status based on an 8-point ordinal scale, and proportion of subjects with categorical PaO₂/FiO₂ ratio endpoints will be conducted using logistic regression model with treatment group and adjusting for relevant baseline prognostic covariates.

The number of days in ICU/CCU (either on or off mechanical ventilation and/or ECMO) at Day 28, number of days on mechanical ventilation and/or ECMO at Day 28 will be analyzed using the analysis of covariance (ANCOVA).

Change in PaO₂/FiO₂ ratio to day 28, change in resting SpO₂ adjusted by FiO₂ to day 28, change in (non-invasive) oxygen supplementation requirements to day 28 will be analyzed using Mixed Model for Repeated Measures (MMRM) approach using relevant prognostic factors as covariates and treatment and Time and treatment *time interaction

The analysis will take into account the inter-current events as follows.

1. Treatment discontinuation (e.g., due to AEs, Withdrawal by Subject or Physician Decision): Missing endpoint will be imputed by the last result prior to discontinuation.

- 2. Death: Composite strategy: inter-current event is taken to be a component of the variable. For number of days not requiring mechanical ventilation at Day 14, number of days in ICU/CCU (either on or off mechanical ventilation and/or ECMO) at Day 28, and number of days on mechanical ventilation and/or ECMO at Day 28; days with missing data after death will be imputed with the worst result until Day 28.
- 3. Treatment discontinuation due to recovering and discharged from hospital: Missing endpoint will be imputed with the last result prior to discontinuation.

Treatment comparison analysis of time to event endpoints, will be performed using cox regression model adjusting for relevant baseline prognostic factors. Hazard ratios together with 95% two-sided confidence intervals for the hazard ratio will be provided.

Time to recovery by Day 28, time to mechanical ventilation/ECMO or all-cause mortality by Day 28, and all-cause mortality at Day 28 (proportion of subjects deceased), and time to death from any cause at Day 28 will be analyzed using Cox regression adjusting for relevant prognostics factors. Other methods will be used as appropriate.

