Proportion of subjects by response category on the NIAID 8-point ordinal scale will be summarized descriptively based on observed data at baseline and Day 28.

Order	Ordinal Level
1	Not hospitalized, no limitations on activities
2	Not hospitalized, limitations on activities and/or requiring home oxygen
3	Hospitalized, not requiring supplemental oxygen, no longer requiring medical care (used if hospitalization was extended for infection-control reasons)
4	Hospitalized, not requiring supplemental oxygen, requiring ongoing medical care (COVID-19-related or otherwise)
5	Hospitalized, requiring supplemental oxygen
6	Hospitalized, requiring high-flow oxygen, non-invasive mechanical ventilation, or both

7	Hospitalized, requiring invasive mechanical ventilation, extra-corporeal membrane oxygenation (ECMO), or both
8	Death
Missing	

9.5 Number of Days in ICU/CCU and Number of Days on Mechanical Ventilation and/or ECMO

Total number of days in ICU/CCU (either on or off mechanical ventilation and/or ECMO) at Day 28 and total number of days on mechanical ventilation and/or ECMO at Day 28 will be summarized descriptively.

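### SAP 9.3 censors subjects who die before recovery as if they could still recover, and names no statistic that can use the censoring

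*SAP*

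**What the plan says.** SAP 9.3 defines three times from randomization, each by Day 28: to recovery, to mechanical ventilation/ECMO or death, and to death.

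- **Recovery.** "Subjects without the event will be censored at the date of last NIAID 8-point ordinal scale assessment". No separate sentence covers a subject who dies before recovering.
- **Ventilation/ECMO or death.** For subjects without the event, "the last known assessment date of mechanical ventilation/ECMO use or survival status, whichever later will be defined as the censoring date".
- **Death.** "For subjects who are alive, the recorded date of last known alive, last contact date, or the date of the last clinic visit", whichever is latest, sets the censoring date.
- **Summary.** "The number of days of the above endpoints will be summarized descriptively as appropriate". No estimator is named.

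SAP 5.1 supplies the general toolkit: "Continuous variables will be summarized using descriptive statistics: n, mean, standard deviation (SD), standard error (SE), median, 25th and 75th percentile, minimum, and maximum". It also states: "There will be no treatment comparison analysis performed for this early terminated study". Protocol (Amendment 1.0) section 9.4 had planned otherwise: "Treatment comparison analysis of time to event endpoints, will be performed using cox regression model".

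Three other places bear on death. Protocol 9.4 imputes the worst result after death, but only for named day counts; time to recovery is not among them. SAP section 9 opens by limiting efficacy summaries to observed data and ruling out imputation of missing endpoints. SAP 9.4 tabulates the ordinal scale, which "will be summarized descriptively based on observed data at baseline and Day 28", with both a Death level and a Missing row.

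**The concern.** Death is not a form of non-informative loss to follow-up for recovery. A dead subject cannot recover, whereas a censored subject is assumed to have the same future chance of recovery as those still under observation. Applying the SAP's only censoring sentence to a subject who dies on, say, Day 6 removes that subject from the risk set. The later recoveries are then spread over a smaller denominator, and estimated recovery rises because someone died.

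The documents do not clearly prevent this. Protocol 6.2 asks for daily scoring to Day 28 and makes death category 8, but does not say that category 8 continues to be recorded after the day of death. If it is recorded once, the last assessment is the death day. If it is recorded daily to Day 28, the same sentence gives Day 28 and the problem disappears. SAP 9.4 depends on the same unstated convention: on observed data, an early death could appear at Day 28 under Death or under Missing.

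The choice of statistic is also open. Cox regression would have used the censored times. Its replacement does not say what does. At stake is whether two programmers would produce the same recovery table, and whether that table would count deaths in a way that flatters recovery.

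**Working it through.** The plan states no figure on this point, so there is nothing to reproduce first. The check is an illustration. The SAP does not report deaths, recovery days or numbers by arm.

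**Inputs**
- 22 subjects randomized (SAP 1), 1:1 allocation (SAP 3): 22/2 = 11 per arm, assumed.
- Assumed: 7 of 11 recover, on Days 5, 7, 9, 11, 13, 16 and 20; 4 do not. Apart from death, nobody leaves before Day 28.
- Horizon: Day 28 (SAP 9.3).

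**Step 1. Statistics listed in SAP 5.1.** Among recovered subjects the mean is (5+7+9+11+13+16+20)/7 = 81/7 = 11.6 days. It is the same whether none or all of the other four die, so it makes no use of their censoring dates.

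**Step 2. Kaplan-Meier with deaths kept as not recovered to Day 28.** All 11 subjects, less earlier recoveries, stay at risk at each recovery day:

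S(28) = 10/11 × 9/10 × 8/9 × 7/8 × 6/7 × 5/6 × 4/5 = 4/11.

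Recovery = 1 − 4/11 = 7/11 = 63.6%, the actual proportion.

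**Step 3. Kaplan-Meier with deaths censored at death.**

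If k deaths all precede the first recovery on Day 5, the risk set starts at 11 − k and recovery is 7/(11 − k):
- k = 1: 7/10 = 70.0%
- k = 2: 7/9 = 77.8%
- k = 3: 7/8 = 87.5%

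If the deaths are spread out:

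| Death days | S(28) | Recovery |
|---|---|---|
| 6 | 10/11 × (8/9 × 7/8 × 6/7 × 5/6 × 4/5 × 3/4) = 10/11 × 3/9 = 0.303 | 69.7% |
| 4, 10 | (9/10 × 8/9 × 7/8) × (5/6 × 4/5 × 3/4 × 2/3) = 7/10 × 2/6 = 0.233 | 76.7% |
| 4, 6, 10 | 9/10 × 7/8 × 6/7 × 4/5 × 3/4 × 2/3 × 1/2 = 0.135 | 86.5% |

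If all deaths fall after Day 20, every risk set is as in Step 2 and the result stays at 63.6%. Over all death days the shift therefore runs from 0 to 87.5 − 63.6 = 23.9 points, and it is never downward.

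**Step 4. Are the two remedies the same?** With no other early censoring, cumulative incidence with death as a competing event also gives 7/11. With earlier withdrawals the two differ. Take four subjects: death Day 2, withdrawal Day 3, recovery Day 5, one unrecovered at Day 28.
- Death kept at risk to Day 28: three at risk on Day 5, recovery 1/3 = 0.333.
- Cumulative incidence: 3/4 × 1/2 = 0.375.

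The SAP has to choose one.

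**Step 5. Does censoring beyond Day 28 matter for the other two endpoints?** Assume deaths on Days 8 and 19, with the other 9 of 11 known alive past Day 28. Kaplan-Meier death at Day 28 is 2/11 = 18.2% whether they are censored at Day 28 or later. Assume composite events on Days 3, 6 and 9. The Day-28 value is 3/11 = 27.3% either way.

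**The case against.** The strongest reply is that the SAP need not be read this way. Death is a level of a scale scored daily to Day 28, and SAP 9.4 tabulates Death at Day 28, which suggests that deaths are meant to be retained. If only observed recoveries are summarized, censoring dates are not used at all and deaths do not alter the summary (Step 1). The largest shift needs three of 11 subjects to die before anyone recovers, on invented data. Dropping Cox regression is a natural result of stopping at 22 subjects.

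Much of this stands, and it limits the size of the point. It does not remove it. Neither document says that category 8 is carried forward, and SAP section 9 rules out imputation. An events-only summary avoids the distortion by saying nothing about subjects who did not recover. It also leaves the defined censoring dates with no use.

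A reader might infer two stronger points, and neither is supported.

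- **Averaged censoring days.** A programmer could average them with event days, so that early deaths would shorten mean time to recovery. The observed-data and no-imputation wording in SAP section 9 weighs against that, and where the SAP wants a time summarized as a plain continuous variable (SAP 8.2, exposure) it says so. No figure based on that reading is used here.
- **No truncation.** The composite and death rules take the latest known date, and follow-up can run to about Day 56 (28 days after a Day 28 dose). This looks like an error, but only events by Day 28 count, so later censoring cannot change a Day-28 estimate (Step 5). Nor does the death rule's wording for subjects who are alive, which does not clearly place a death after Day 28, affect any Day-28 result. Both are matters of wording.

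**Conclusion.** The concern holds, at minor severity. As worded, SAP 9.3 treats a subject who dies unrecovered as still able to recover. The SAP 5.1 statistics cannot use the resulting times, and a Kaplan-Meier summary under this rule would overstate recovery if any death precedes a later recovery. On the assumed arm of 11 with 7 recoveries, 63.6% becomes at most 70.0%, 77.8% or 87.5% with one, two or three early deaths, and is unchanged if deaths follow the last recovery.

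This rests on category 8 not being scored daily to Day 28 after death, which the documents leave open, and on a censoring-based estimator being chosen as the appropriate summary. It does not show that any reported result is biased. The consequences are contained: the endpoints are secondary and descriptive, 22 subjects were randomized, there is no treatment comparison, Day-28 mortality is summarized separately (SAP 9.2), and all data and deaths are listed (SAP 5 and 10.1).

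**What to change.** In SAP 9.3:

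1. State that a subject who dies before recovery counts as not recovered through Day 28, and name one method. Cumulative incidence of recovery with death as a competing event is preferable. Keeping deaths at risk to Day 28 is workable but gives a different answer when others are censored earlier (Step 4).
2. State, for both 9.3 and 9.4, that category 8 is carried from the day of death to Day 28 as a known state and not as an imputation. Early deaths then appear in the Death row and not under Missing.
3. Replace the open-ended descriptive summary with cumulative-incidence or Kaplan-Meier estimates by arm, with the number of events and of subjects at risk.
4. As a clarification only, cut the composite and death times at Day 28 and censor later events there. Day-28 estimates do not change.

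The cost is a few lines of SAP text and standard programming, with no change to data collection. With about 11 subjects per arm, intervals will be wide and some medians may not be reached.

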4.4. Study Duration

The Screening Period is up to 2 days prior to randomization, to confirm eligibility.

The Treatment Period is 28 days. Study drug will be administered as IV infusion on Days 1 (day of randomization), 7, 14 and 28.

The Follow-Up Period is 28 days after the last dose.

Visits /assessments will occur every day for 28 days, or until hospital discharge, whichever occurs earlier. If a subject is discharged prior to Day 14 or Day 28, the subject should return as outpatient on Days 14 and/or Day 28, for study drug infusions and assessments. For subjects who cannot return for an in-person visit, study assessments maybe done remotely, such as via phone.

Subjects who discontinue study treatment prior to Day 28 are encouraged to remain in the study to complete all remaining visits and assessments, including for collection of vital status. Subjects

who discontinue treatment, for any reason, will need to return for an Early Treatment Discontinuation visit 28 days (+7 Days) after the last infusion and may be contacted by phone at Day 14 and 28 to check the subject's survival status.

See also Section 5 and 6 for additional detail.

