6.2. Modified WHO Ordinal Scale

Assessment of clinical status, using an 8-Point, Modified WHO Ordinal Scale as specified below, should be assessed daily, until Day 28:

- 1. Not hospitalized, no limitations on activities
- 2. Not hospitalized, limitations on activities and/or requiring home oxygen
- 3. Hospitalized, not requiring supplemental oxygen, no longer requiring medical care
- 4. Hospitalized, not requiring supplemental oxygen, requiring ongoing medical care (COVID-19-re; ated or otherwise)
- 5. Hospitalized, requiring supplemental oxygen
- 6. Hospitalized, requiring nasal high-flow oxygen, non-invasive mechanical ventilation, or both
- 7. Hospitalized, requiring invasive mechanical ventilation, extra-corporeal membrane oxygenation (ECMO), or both
- 8. Death

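### SAP 9.3 censors time to ventilation/ECMO or death at the later of two dates, so follow-up with only survival known counts as ventilation-free; the effect is confined to a descriptive secondary endpoint in 22 subjects

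*SAP*

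**What the plan says.** SAP 9.3 defines the endpoint as "Time (number of days) from randomization to mechanical ventilation/ECMO or all-cause mortality by Day 28". For subjects without the event, "the last known assessment date of mechanical ventilation/ECMO use or survival status, whichever later will be defined as the censoring date". In the same section, time to recovery is censored at the last assessment of its own ordinal scale, and time to death at the latest date known alive. SAP 9.3 then summarizes the days descriptively, and SAP 5.1 rules out any treatment comparison.

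The two sources behind the composite are scheduled differently in Protocol Amendment 1, Appendix 1 (Schedule of Assessments):

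- **Ventilation/ECMO.** The oxygen supplementation row carries footnote 3, "Need for mechanical ventilation/ECMO, including ventilator settings, or supplemental oxygen, including mode of oxygen delivery", and footnote 4, "Collected until Day 28 or hospital discharge, whichever occurs earlier".
- **Survival.** The survival, ICU and hospital discharge row has no such stop and runs to the visit four weeks after the last dose. Under footnote 7, for subjects discharged early who will not return, "visits may be conducted remotely for assessment of vital status and safety", and "If a subject is lost to follow-up after hospital discharge, vital status may also be obtained from public records". Section 4.4 adds that subjects who stop treatment "may be contacted by phone at Day 14 and 28 to check the" subject's survival.

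**The concern.** For a composite of ventilation/ECMO or death, being event-free on a given day requires knowing that neither has happened. Taking the later of the two dates lets the survival date alone extend follow-up. A public record can show that a discharged subject is alive; it cannot show whether the subject was readmitted and ventilated. The rule nevertheless counts the whole interval as free of ventilation.

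Any summary built on the censoring date (days at risk, mean time, an event-free curve) then looks more complete than the data are, and any error from unseen ventilation runs towards more event-free time.

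The rule also has no explicit Day 28 limit, although the endpoint is defined to Day 28 and survival is collected after it.

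**Working it through.** **The plan's own figures.** None is given for this endpoint. The only related figure, about 80% power with 65 per arm (65% against 85%, two-sided 10%; Protocol 9.1), is for the primary proportion. It reproduces at 80.1% by full enumeration of Fisher's exact test and does not depend on the censoring rule.

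**How the dates separate.** Take a subject discharged on Day 10 and found alive on Day 28 by public record only. Ventilation status is last known on Day 10. The SAP rule censors on Day 28, crediting 28 − 10 = 18 days without ventilation information.

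**Small-sample illustration (assumed data).** The SAP gives 22 randomized; I assume 11 per arm under 1:1 allocation. Assume events on Days 3, 6, 12 and 18 and seven event-free subjects, of whom k were discharged on Day 10 with vital status only afterwards. The event-free estimate is Kaplan-Meier at Day 28, which the SAP does not name.

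- SAP rule, any k: 7/11 = 63.6%. Person-days 3 + 6 + 12 + 18 + 7×28 = 235; mean 235/11 = 21.4.
- Censoring at last known ventilation status: 9/11 are event-free after Day 6, and 9 − k remain at risk on Day 12. The estimate is (9/11) × (7 − k)/(9 − k), with person-days 235 − 18k.

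| k | Event-free at Day 28 | Person-days | Mean days |
|---|---|---|---|
| 1 | (9/11)(6/8) = 61.4% | 217 | 19.7 |
| 3 | (9/11)(4/6) = 54.5% | 181 | 16.5 |
| 5 | (9/11)(2/4) = 40.9% | 145 | 13.2 |

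The SAP rule gives the same answer for every k, so it conceals the loss of information. The table does not show which column is nearer the truth; that depends on what happened after Day 10.

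**Possible bias (assumed constant hazard).** Borrow the protocol's 65% placebo assumption as the Day 28 event-free probability: λ = −ln(0.65)/28 = 0.01539 per day, exp(−10λ) = 0.8574, exp(−18λ) = 0.7581. Let a share g have vital status only from Day 10, with all their later events being unseen ventilation. The SAP rule then estimates 0.8574 × [g + (1 − g) × 0.7581].

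| g | SAP rule | Truth if their later hazard equals the rest | Truth if it is half |
|---|---|---|---|
| 10% | 67.1% | 65.0% | 66.0% |
| 20% | 69.1% | 65.0% | 66.9% |
| 30% | 71.2% | 65.0% | 67.9% |
| 50% | 75.4% | 65.0% | 69.8% |

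The overstatement is 2.1 to 10.4 points at equal hazard and 1.1 to 5.6 points at half. At zero hazard there is none. Censoring at last known ventilation status gives 65.0% throughout: correct at equal hazard, too low otherwise.

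**The case against.** **Little rests on the date.** There are 22 subjects, no treatment comparison, no named survival-curve or Cox analysis in the SAP, and a descriptive summary of days. This stands and sets the weight of the point.

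**Other sources cover many discharged subjects.** The ordinal scale "should be assessed daily, until Day 28" (Protocol 6.2) includes a category for invasive ventilation/ECMO and is scheduled at Days 14 and 28, although Appendix 1, footnote 6, drops the visits between infusions after discharge. The ICU and hospital status row continues after discharge, SAE reporting should capture a readmission, and Section 4.4 allows assessments to be done remotely. SAP 5.3 refers to ventilation start and stop times, which suggests a dated record. This stands for subjects still in contact. It does not help for those known only through a public record or a survival-only call.

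**The alternative is not unbiased.** Discharge predicts outcome, so censoring survivors there is informative. Counting deaths learned later while censoring survivors early worsens this. Assumed example: 11 subjects, four events before Day 10, one death on Day 20 after discharge, and six survivors never ventilated, three of them discharged on Day 10 with vital status only. The true event-free proportion is 6/11 = 54.5%. The SAP rule gives (7/11)(6/7) = 54.5%; the earlier date gives (7/11)(3/4) = 47.7%. This stands, and is why the present rule should remain as a second summary.

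**Conclusion.** The point holds as a specification error of limited reach. The censoring rule treats survival-only follow-up as proof of freedom from ventilation, an assumption that the SAP does not state. Its size in this trial cannot be given, because the documents do not show whether any of the 22 subjects had vital status only. The percentages above rest on assumed event times, discharge days and hazards.

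Three stronger readings are tempting and are not supported:

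- *A reader might infer that the primary endpoint is distorted by this rule.* SAP 9.1 is a proportion on observed data and uses no censoring date.
- *A reader might take one missed ventilation in an assumed arm of 11 (1/11 = 9.1 points) as the size of the error.* That event is missed under either rule; changing the censoring date does not recover it.
- *A reader might infer a biased treatment comparison.* None is performed.

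**What to change.** In SAP 9.3, replace the later-of-two-dates rule with this: censor at the last date on which the subject was known to be free of both components, capped at Day 28, and count a death by Day 28 as an event. Any source that shows ventilation status may set the date, including the ordinal scale, ICU/hospital status and SAE records. Report by arm the number of subjects with vital status only after their last known ventilation status. Keep the present rule, also capped at Day 28, as a sensitivity summary beside the main one.

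The cost is one sentence in the SAP, one count and one extra summary, all from data already collected. The downside is that earlier censoring of discharged survivors may understate event-free survival, so neither summary should be shown alone.

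A new question in the protocol's schedule would not help this trial. It was terminated on 19 February 2021. A subject randomized that day would reach Day 28 on 18 March and the four-week follow-up on 15 April, before the SAP approvals of 26 April to 3 May 2021 (assuming no later randomization).
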